4.5.2. Follow-Up Assessments

Refer to 4.5.1. For comparator group, follow-up assessments are performed per standard of care and IRR information will be collected from the medical records.

4.6 Discontinuation of Protocol-Specified Therapy

Protocol-specified therapy may be discontinued for any of the following reasons:

- Unacceptable toxicity
- Patient election to discontinue therapy (for any reason)
- Physician's judgment

4.7 Subject Discontinuation

Patients will be withdrawn from the study if they get pregnant during the treatment period or withdraw consent. If patients discontinue ocrelizumab for any reason they will be asked to continue the study assessments per protocol until end of study for safety assessments. Patients in the switching group who withdraw from the study before their first infusion at 6 months will be replaced.

The reason for premature discontinuation of a subject will be recorded on the Case Report Form.

4.8 Study Discontinuation

Genentech Study Center, and the Principal Investigator has the right to terminate this study at any time. Reasons for terminating the study may include the following:

- The incidence or severity of adverse events in this or other studies indicates a potential health hazard to subjects
- Subject enrollment is unsatisfactory
- Data recording are inaccurate or incomplete
- Study protocol not followed

4.9 STATISTICAL METHODS

4.9.1 Analysis of the Conduct of the Study

The study will consist of a convenience sample of eligible MS patients at the Rocky Mountain MS Center who are currently active patients and are taking rituximab for the treatment of their MS.

We will keep track of the number enrolled in each study group and log any protocol deviations, lack of compliance, no shows or drop outs. Frequencies and proportions will be presented and compared between treatment groups.

4.9.2. Analysis of Treatment Group Comparability

As described in section 4.2, demographic variables and measures of baseline disease severity, including age, gender, MS disease duration, baseline PDDS, type of MS at baseline (first infusion in both study groups), along with discontinuations, will be recorded and compared between treatment groups. All available observations will be used. For continuous variables (age, MS disease duration), by treatment group means, standard deviations, medians, and ranges will be recorded, and differences among treatment groups will be tested for with either with T-test/ANOVA methods or Wilcoxon/Kruskal Wallis tests. For categorical variables (gender, type of MS, disability, discontinuations), frequencies and proportions will be presented, and differences among treatment groups will be tested for using chi-square/Fisher's exact test.

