4.1.2 Inclusion Criteria

Switching group:

- Current active patient of RMMSC
- 18-65 years
- Diagnosis of relapsing forms of MS
- Completed **≥ two doses** of rituximab with the last dose having been administered:
 - a) within 12 months of screening
 - and
 - b) at least 6 months prior to first planned infusion of study drug
- Are receiving their current infusions of rituximab at the University of Colorado Outpatient Infusion Center
- Have discussed the possibility of switching to ocrelizumab with their MS provider
- Screened for Hepatitis B and C and TB within 2 years of first dose of ocrelizumab
- A negative serum pregnancy test must be available for premenopausal women and for women <12 months after the onset of menopause, unless they have undergone surgical sterilization.
- Women of childbearing potential must agree to use a “highly effective”, hormonal form of contraception or two “effective” forms of non-hormonal contraception. Contraception must continue for the duration of study treatment and for at least three months after the last dose of study treatment
- Are able to complete patient reported outcomes developed as English written scales.
- Must be able and willing to give meaningful, written informed consent prior to participation in the trial, in accordance with local regulatory requirements

Comparator group:

- Current active patient of RMMSC

- 18-65 years
- Diagnosis of relapsing forms of MS
- Completed \geq **two doses** of rituximab with the last dose having been administered within 12 months of screening as standard of care
- Are receiving their current infusions of rituximab as standard of care at the University of Colorado Outpatient Infusion Center and will continue to do so
- Are willing to be followed for subsequent rituximab infusions during the study period as standard of care, and/or allow retrospective data collection on previous rituximab infusions
- Must be able and willing to give meaningful, written informed consent prior to participation in the trial, in accordance with local regulatory requirements

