4.5.1 Assessments during Treatment

The following evaluations will be conducted during and post treatment:

Study Visits and Procedures Summary:

Study visits for the switching group include a) screening visit, b) first infusion of 300 mg of ocrelizumab (day 1 or T₀), c) 300 mg of ocrelizumab infusion on day 15 (T₁), d) 600 mg of ocrelizumab at 6 months (+/- 2 weeks) after day 1 (T₂) and, e) a research termination visit between month 12 and 18 - (+/- 2 weeks)(T₃). In some cases, screening procedures may be performed on the first infusion day rather than as a separate visit. The patient may continue on 600 mg of ocrelizumab or (if the patient prefers) 500mg rituximab at T₃, or 12 to 18 months after Day 1 (T₀). A month is defined as 28 days. Study visits for the comparator group include only standard of care infusion of rituximab, up to two infusions per patient, approximately 6 months apart. Research data on IRRs for the comparator group will be collected from the medical records.

A summary of all procedures for switching group is outlined under “Schedule of Events” in **Table 1** below. During the screening visit, patients will be consented for the study and receive both a medical and full neurological exam. Verification of their hepatitis B and C status including testing will be conducted if a patient has not been tested in the last two years. MS disease history and demographic information will also be collected. Patients will also receive an EDSS exam and take an online version of the PDDS (done as standard of care- on an iPad).

The Expanded Disability Status Scale (EDSS) is a commonly used assessment that allows clinicians to objectively measure changes in the disability status of MS patients using unbiased clinical raters.⁷ The **EDSS** provides a total score on a scale that ranges from 0 to 10. The first levels 1.0 to 4.5 refer to people with a high degree of ambulatory ability and the subsequent levels 5.0 to 9.5 refer to the loss of ambulatory ability. The range of main categories include (0) = *normal neurologic exam*; to (5) = *ambulatory without aid or rest for 200 meters; disability severe enough to impair full daily activities*; to (10) = *death due to MS*. In addition, it also provides seven subscale measurements called Functional System (FS) scores.

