4.9.4 Safety Analysis

The default analysis will be available case for all eligible participants on an intent to treat basis. Alpha = 0.05 for all tests. As in the OPERA I and II randomized clinical trials, the primary and secondary end points will be descriptively presented. Frequencies and percentages for the severity of IRR grades (Grades 0-5) will be presented for both study groups following each infusion time point and overall between groups. 95% confidence intervals for the proportions will be calculated. Differences in the distribution of IRR severity grades between independent samples (i.e. comparison between groups at a common time point) will be tested with the chi-square or Fisher's exact association test, and additionally with ordinal or multinomial logistic regression. If sample sizes are small among some levels of IRR severity grades, they may be collapsed or dichotomized (i.e. Grade 3 or higher, any reaction or no reaction, severe reaction or none as examples) and methods described for binary outcomes under secondary endpoints will be utilized. Dichotomization may be used to make analysis and presentation of results more manageable as well.

The primary endpoint will be the proportion of whether any IRR occurred (yes or no) per infusion cycle per patient in each study group. The secondary endpoints include the proportion per infusion per patient of severe infusion reaction (grade 3 or greater), the proportion of infusion reactions and severe infusion reaction per patient across all infusions, the proportion patients with anti-drug antibodies, and the proportion of patients with depleted B cells. The primary outcome, binary occurrence of IRR per infusion per patient, could be analyzed with logistic or relative risk models, with GEE (generalized estimating equations) and/or GLMM

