4.9.6 Determination of Sample Size

The sample size will be a convenience sample. It is anticipated a minimum of 100 patients will qualify for each cohort (200 total) resulting in studying 300 infusions with ocrelizumab and 200 infusions with rituximab. This is an observational study not designed to demonstrate superiority of ocrelizumab over rituximab in efficacy but instead indicate the magnitude of the relative tolerability and immunogenicity. The primary endpoint is the difference in the percentage of IRRs between the two study groups. In addition, both study groups will include treatment experienced patients on rituximab who have experienced a minimum of two infusions and either continue to stay on rituximab or switch to ocrelizumab.

To estimate study power with the proposed sample size of 100 infusions in each group, we conducted a chart review of 50 patients at the Rocky Mountain MS Center who are currently taking rituximab and examined their IRRs using the proposed IRR grading scale (see section 3.3.1) from Grade 0-5. The number and severity of IRRs were captured following their third rituximab infusion. The highest grade of an IRR that occurred during the infusion was recorded. Our pilot data revealed that following the third rituximab infusion, 14.3% of patients had an IRR of which 85.71% were Grade 0, 12.24% were grade 2 and 2.05% were Grade 3. Hauser et al., found that following the second infusion of rituximab in patients, the majority of whom (60%) were not taking a DMT for 6 months prior to initiating rituximab only 20.3% experienced in an IRR.³

Using IRR estimates from our pilot data and establishing a clinically meaningful difference of 20% increase in IRRs, we conducted the following power analysis for a sample of 95 patients (assuming a 5% attrition rate after recruiting 100 patients in each study group). An IRR proportion for ocrelizumab users at 34.3% compared with 14.3% for rituximab (obtained from our pilot data) for a two sided (alpha = 0.05) two sample proportion test for the null hypothesis of no difference between rituximab and ocrelizumab in proportion of IRRs would result in 90% power for 95 patients per group.

In response to the FDA IND letter, “the power analysis in Section 4.9.6 of the protocol appears to compare the infusion-related reaction (IRR) rate at the third rituximab infusion (14.3%) to that of the first infusion of OCR (34.3%). Because

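### The crude between-group test of discontinuations compares groups with unequal time at risk and can show a false excess on ocrelizumab

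*Combined protocol and SAP*

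**What the plan says.** Sections 4.2 and 4.9.2 place discontinuations beside age, gender, MS duration and type of MS: these, "along with discontinuations, will be recorded and compared between treatment groups". Discontinuations are classed as categorical, and for such variables "differences among treatment groups will be tested for using chi-square" or Fisher's exact test. Section 4.9.4 sets "Alpha = 0.05 for all tests". Section 4.9.1 adds drop-outs to a conduct log: "Frequencies and proportions will be presented and compared between treatment groups". It names no test. None of these sections gives a definition of discontinuation, a common window, person-time or a time-to-event method.

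Follow-up differs by group. Under section 4.5.1, switchers have infusions on day 1, day 15 and at 6 months, then "a research termination visit between month 12 and 18" (T3). Section 4.7 asks those who stop ocrelizumab to stay in the study to its end. Comparators have routine rituximab infusions only, "up to two infusions per patient, approximately 6 months apart", and no termination visit is described for them. The comparator inclusion criteria in section 4.1.2 require that rituximab will go on. They also require willingness to be followed "and/or allow retrospective data collection on previous rituximab infusions", so a patient can qualify on past infusions alone. Section 3.1 allows retrospective collection only after consent.

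**The concern.** A crude proportion is a fair comparison only if both groups had the same opportunity to have the event. Here switchers can be counted as discontinuing over two to three times as long as comparators. A retrospective-only comparator cannot be counted at all, because the data are already complete when consent is given. Requiring comparators to be continuers lowers their count further. All three features push the difference the same way, towards more discontinuations on ocrelizumab.

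The test is also in the wrong place. A comparability table should describe patients as they were before treatment, whereas discontinuation comes afterwards and may be a consequence of the drug. Because the study is about tolerability, a significant difference in that table could be taken as a finding about ocrelizumab.

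**Working it through.** **The plan's own figures.** The documents give no figure for the discontinuation comparison. The only related calculation is the IRR power statement in section 4.9.6: 34.3% v 14.3%, 95 per group, "two sided (alpha = 0.05) two sample proportion test". With pooled variance under the null this gives power of 0.901, matching the stated 90%. Dividing 95 by 0.95 gives the 100 recruited per group. The IRR calculation reproduces. It is also the source of the 5% attrition figure, which has no time period attached.

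**Inputs.**
- Switching group 100, comparator group 100 or 200 (section 4.1).
- Switchers at risk 12 or 18 months; comparators 6 months if prospective, 0 if retrospective-only (sections 4.1.2 and 4.5.1).
- Attrition 5% (section 4.9.6). *Assumed period:* the switchers' whole follow-up, or each 6 months.
- *Assumed retrospective-only share:* none or half. The documents do not state it.

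**Method.** Give both groups the same constant stopping rate. If a proportion r stops in w months, the proportion stopping by month t is 1 − (1 − r)^(t/w). Then sum the exact binomial probabilities of all outcomes for which the two-sided 0.05 Fisher test is significant with the excess on ocrelizumab. The nominal value is 2.5%.

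**Expected proportions.**
- 5% over 12 months: switchers 5.0%; comparators at 6 months 1 − 0.95^(1/2) = 2.5%.
- 5% over 18 months: switchers 5.0%; comparators 1 − 0.95^(1/3) = 1.7%.
- 5% per 6 months: switchers 1 − 0.95² = 9.75% at month 12 and 1 − 0.95³ = 14.3% at month 18; comparators 5.0%.

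**Chance of a false excess on ocrelizumab (Fisher).**

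| Scenario | 100 v 100 | 100 v 200 |
|---|---|---|
| 5% is switchers' total over 12 months, all comparators followed 6 months | 6.5% | 18.2% |
| 5% is switchers' total over 18 months, all followed 6 months | 11.9% | 33.9% |
| Total over 12 months, half retrospective-only | 16% | 46% |
| Total over 18 months, half retrospective-only | 22% | 59% |
| 5% per 6 months, switchers to 12 months, all followed 6 months | 17.4% | 31.1% |
| 5% per 6 months, switchers to 18 months, all followed 6 months | 52.6% | 73.8% |

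The uncorrected chi-square test, which the plan also allows, gives higher values: 12.7% and 20.8% for the first row.

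**Low end.** If 5% is spread over 18 months but T3 falls at month 12, the expected proportions are 3.4% v 1.7%. Fisher then gives 2.9% at 100 v 100, which is negligible inflation (chi-square 9.7%), and 14.3% at 100 v 200.

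**If discontinuation means stopping protocol drug.** The last protocol infusion is at month 6, so both windows are about 6 months. With 5% in each group and all comparators prospective, the chance is 1.0% at 100 v 100 and 2.2% at 100 v 200. With half the comparators retrospective-only it is about 7% and 19%.

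**After the fix.** One 6-month window and prospective patients only is that same all-prospective case: 1.0% or 2.2% with Fisher, 2.2% or 2.8% with chi-square, at or near nominal.

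**The case against.** Four points can be made on the other side.

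1. *The size depends on how the 5% is read.* This stands. Section 4.9.6 gives 5% as overall attrition. Compounding it every 6 months produces two to three times the planned figure in switchers. A reader might infer from the largest values above that a false excess is likely. The documents do not support that: with 5% as the switchers' total, it becomes likely only with 200 comparators and a large retrospective-only share, and no such share is given.

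2. *The term is undefined.* This also stands. If it means stopping protocol therapy, the 12-to-18 v 6 month contrast largely disappears, leaving only the retrospective-only patients and the selection of continuers. In addition, section 4.3.1 accepts rituximab infusions within a 12-month window, so some comparators may be followed for longer than 6 months, and section 4.9.5 suggests that free treatment should keep switchers in the study. Either would reduce the distortion.

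3. *Discontinuation is not an endpoint.* Correct; sections 3.3 and 4.9.4 do not list it as one. The caution in section 4.2 about limited interpretation concerns adverse events and IRRs, however, and does not reach discontinuations.

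4. *Nothing says discontinuation will be adjusted for.* A reader might infer that an imbalance would bring it into the regression or propensity model. Sections 4.2 and 4.9.4 name only age, MS duration and baseline EDSS or PDDS. Those lists are open-ended, but adjustment for discontinuation is not planned and should not be alleged.

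What remains is that the test, followed as written, compares unequal opportunities and sits among baseline variables.

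**Conclusion.** The concern holds as a minor one. With equal true stopping rates, the planned test can show a false excess of discontinuations on ocrelizumab. With 5% as the switchers' total and all comparators followed 6 months, the chance is about 6.5 to 12% at 100 v 100 and 18 to 34% at 100 v 200. It rises to 16 to 22% and 46 to 59% if half the comparators are retrospective-only. At 5% per 6 months with all comparators followed 6 months, it is 17 to 53% and 31 to 74%. If the term means stopping protocol drug by month 6, inflation comes only from retrospective-only comparators (about 7% or 19% if they are half) and from the selection of continuers, which these figures do not quantify.

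The equal constant rate, the attrition period and the retrospective share are assumptions. The IRR primary endpoint and its power calculation are unaffected, so nothing here should be read as undermining the main comparison.

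**What to change.** - **Sections 4.2 and 4.9.2:** remove discontinuations from the comparability variables and their tests.
- **Section 4.9.1:** define discontinuation, stating whether it means stopping the drug or leaving the study. Compare it only among prospectively consented patients, over one common window from the first study infusion to the next scheduled infusion at about 6 months.
- **Reporting:** show retrospective-only comparators separately as not at risk. Describe switcher discontinuations after month 6 without a between-group test. Tabulate reasons descriptively where they are recorded.

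The change is one of wording, with no new visits or patients. The cost is fewer comparators in this comparison. Section 4.7 has reasons for premature discontinuation recorded on the CRF, but the comparator data collection described in sections 4.5.1, 4.5.2 and 5.1 covers IRRs, relapses and SAEs. Complete comparator reasons would therefore need an added chart item. With few events expected, a formal split by reason would tell little, so a descriptive table is enough.

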4.9.3 Efficacy Analysis –Not Applicable

a. Primary Endpoint: NA

b. Secondary Endpoints: NA

4.9.4 Safety Analysis

The default analysis will be available case for all eligible participants on an intent to treat basis. Alpha = 0.05 for all tests. As in the OPERA I and II randomized clinical trials, the primary and secondary end points will be descriptively presented. Frequencies and percentages for the severity of IRR grades (Grades 0-5) will be presented for both study groups following each infusion time point and overall between groups. 95% confidence intervals for the proportions will be calculated. Differences in the distribution of IRR severity grades between independent samples (i.e. comparison between groups at a common time point) will be tested with the chi-square or Fisher's exact association test, and additionally with ordinal or multinomial logistic regression. If sample sizes are small among some levels of IRR severity grades, they may be collapsed or dichotomized (i.e. Grade 3 or higher, any reaction or no reaction, severe reaction or none as examples) and methods described for binary outcomes under secondary endpoints will be utilized. Dichotomization may be used to make analysis and presentation of results more manageable as well.

The primary endpoint will be the proportion of whether any IRR occurred (yes or no) per infusion cycle per patient in each study group. The secondary endpoints include the proportion per infusion per patient of severe infusion reaction (grade 3 or greater), the proportion of infusion reactions and severe infusion reaction per patient across all infusions, the proportion patients with anti-drug antibodies, and the proportion of patients with depleted B cells. The primary outcome, binary occurrence of IRR per infusion per patient, could be analyzed with logistic or relative risk models, with GEE (generalized estimating equations) and/or GLMM

(generalized linear mixed models) methods to incorporate correlation on repeated infusions on a patient. The same method will apply to other longitudinal binary outcomes. Poisson or negative binomial models with exposure terms could calculate rates of IRR per infusion per patient as a counting process. Similar methods will be used to compare IRR rates between the switching group and OPERA I and II phase 3 clinical trials. The total number of IRRs experienced in each patient, will be analyzed with Poisson or negative binomial models. Paired T tests will be used to assess differences in specific cytokine markers between pre and post infusion at each infusion cycle. Patient reported outcomes will also be reported descriptively. Frequencies and proportions will be reported for adverse and serious events and loss to follow up

As contingency methodology, exact tests and confidence intervals for measures of association between categorical variables can be utilized when necessary, if the sample sizes for some of the cells are small. Transforms or rank based methods, such as Wilcoxon sign rank, can be used in place of the T-test if deviation for normality is severe. Otherwise the T-test is a robust test of mean differences for medium to large sample sizes. If matching leads to good balance between the treatment groups on the demographic and disease variables, including age, MS disease duration, and baseline PDDS score, then confounding will not be an issue and the proposed unadjusted tests should be adequate. Alternatively, if the demographic and disease variables are not balanced, then regression or propensity score methods will be used to adjust for potential confounding. Sensitivity analysis comparing unadjusted and adjusted results will be used to determine the extent of the confounding effect. Adjustment for covariates can sometimes improve the precision of the estimated treatment difference by reducing random noise in the outcome.

Separate descriptive statistics will be presented for relapsing and progressive MS patients. Similar descriptive analysis will be conducted for subgroups according to age (in tertiles) and baseline disability (mild, moderate, severe) as measured by baseline PDDS score. However, the study is not powered for subgroup analyses and no inferences for subgroups or interactions are planned. As the sample is one of convenience, the study is generalizable to the extent patients at the Rocky Mountain MS center who are willing to participate are representative of MS patients.

With only one primary endpoint, adjustment for multiple comparisons will not be much of an issue. Secondary endpoints will be tested univariately. The study is not powered for multiple tests with control of the family-wise error rate. Bonferroni, iterative Bonferroni, false discovery rates, and, in some cases, protective overall tests could also be used if adjustment for multiple tests is desired.

All adverse events, lack of compliance, protocol violations, and drop outs will be logged, and frequencies and proportions will be presented. Safety will be assessed at each infusion.

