4. MATERIALS AND METHODS

4.1 Subjects

We plan to enroll 100 patients in the switching group and between 100 and 200 patients in the comparator group (to study 200 infusions) for a total of up to 200-300 patients which would provide adequate power (90%) for the study. To account for screen failures and withdrawals, we are seeking to enroll an additional 50 patients for a total of 250-350 patients. Patients are not confined to only one of the 2 groups. For example, data may be collected from a patient as part of the rituximab arm and then at a later point the patient decides to switch to ocrelizumab. This patient could then be consented into the switching group. Enrollment will occur over a 3-month period at RMMSC.. Dropouts in the switching group that occur prior to the 6 month infusion will be replaced. All patients will be included in the analyses (Intent to Treat Analysis).

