4.2 Method of Treatment Assignment

The study will not be a randomized trial. Patients will not be assigned to the switching group, but rather will be enrolled after a clinical decision has been made with their provider about whether they will continue on rituximab or switch

to ocrelizumab. The following steps will be taken to minimize potential biases in sample selection.

First, in an effort to impose some degree of similarity between the treatment groups, control patients will be matched, either 1:1 or 2:1 depending on the number of control patients, with switching patients on gender and age (+/- 2 years) at recruitment. The demographic information on switching patients will be scanned to find matches for the patients in the non-switching group.

Furthermore, screening of additional patients beyond the 200 required for enrollment in the non-switching group will be also conducted to ensure the best possible matches. Second, baseline statistics will be monitored as patients enter the study, and selection of patients may be modified in order to maintain relative balance between treatment groups (if necessary using measures of disease severity other than age and gender) if we are able to overenroll the number of non-switchers. Third, demographic variables and measures of baseline disease severity, including age, gender, MS disease duration, type of MS at baseline (first infusion in both study groups), along with discontinuations, will be recorded and compared between treatment groups.

All available observations will be used. For continuous variables (age, MS disease duration), by treatment group means, standard deviations, medians, and ranges will be recorded, and differences among treatment groups will be tested for with either with T-test/ANOVA methods or Wilcoxon/Kruskal Wallis tests. For categorical variables (gender, type of MS, disability, discontinuations), frequencies and proportions will be presented, and differences among treatment groups will be tested for using chi-square/Fisher's exact test. Fourth, following these measures, if treatment confounding is found to still be an issue, regression or propensity score methods, with covariates such as age, MS disease duration, and baseline EDSS score will be used post hoc to minimize confounding.

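### Infusion reactions are to be analysed by intent to treat in a non-randomised study that allows drug changes; each infusion should be analysed under the drug infused

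*Combined protocol and SAP*

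**What the plan says.** Section 4.9.4 gives the basis for all the reaction analyses: "The default analysis will be available case for all eligible participants on an intent to treat basis". Section 4.1 says the same in other words: "All patients will be included in the analyses (Intent to Treat Analysis"). The term is not defined in either place, and no as-treated or safety set is described. Section 4.2 states: "The study will not be a randomized trial". Both 3.3.1 and 4.9.4 state the primary endpoint by study group.

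The plan allows the drug to change in three ways:

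- **Early stopping.** Section 4.6 lets ocrelizumab be stopped for toxicity, by patient choice or on the physician's judgment. Section 4.7 adds: "If patients discontinue ocrelizumab for any reason they will be asked to continue the study assessments per protocol until end of study for safety assessments". Nothing says how data are handled if such a patient goes back to rituximab.
- **Contribution to both groups.** Section 4.1: "Patients are not confined to only one of the 2 groups". Its example is a rituximab-arm patient who is later consented into the switching group.
- **Choice at the end.** Section 4.5.1: "The patient may continue on 600 mg of ocrelizumab or (if the patient prefers) 500mg rituximab at" T3.

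Other text counts by drug. The secondary reaction assessments in 3.3.1 refer to ocrelizumab infusions in the switching group and rituximab infusions in the comparator group. Section 4.9.6 plans on 300 ocrelizumab and 200 rituximab infusions.

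**The concern.** An infusion reaction is a response to the drug in the bag. Intent to treat protects a randomised comparison, and here there is none to protect. Applied literally, it fixes a patient's group and carries every later record with it, whatever was infused.

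That leaves two routes to misattribution. A switching patient who stops ocrelizumab after day 1 or day 15 and receives rituximab at month 6 would add a rituximab infusion to the switching group. A graded record would exist, because 3.3.1 has the infusion-centre nurses grade every infusion of either drug. In the other direction, a comparator patient who later switches could have ocrelizumab infusions counted as rituximab. If ocrelizumab has the higher reaction rate, as the plan assumes, both routes shrink the difference, which is the unwelcome direction for a tolerability comparison.

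The laboratory endpoints share the gap. A B-cell sample at T3 from a patient whose last infusion was rituximab reflects rituximab. Two analysts working from this text could also build different primary datasets.

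**Working it through.** **1. The plan's own figure (4.9.6).** Inputs: reaction proportions 14.3% (rituximab) and 34.3% (ocrelizumab), two-sided alpha 0.05, 95 patients per group.

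Power = Φ[(d − 1.96·SE0)/SE1], where SE0 = √[2·p̄(1−p̄)/n] and SE1 = √{[p1(1−p1) + p2(1−p2)]/n}.

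With p̄ = 0.243, SE0 = 0.06223 and SE1 = 0.06052: (0.200 − 0.12197)/0.06052 = 1.289, so power is 90.1%. The stated 90% is reproduced.

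**2. Which graded infusions are exposed.**

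- T0 and T1 are the ocrelizumab infusions through which a patient becomes exposed. A later reversion cannot relabel them.
- T2 (month 6) can be affected if the patient has gone back to rituximab.
- T3 cannot be affected. Table 1 has no nurse-recorded reaction there, and the T3 bloods are listed as a pre-infusion draw.

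So one of three graded infusions is exposed. If a share g of switching patients reverts before T2, the share of switching-group infusions that are rituximab is f = g/3 (three infusions each).

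**3. Dilution in the switching group.** Observed rate = (1 − f)·34.3% + f·14.3%, so the difference is 20.0·(1 − f) points. The documents give no reversion rate; g is assumed.

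| g (assumed) | f | Pooled difference | Power, 95 v 95 |
|---|---|---|---|
| 0 | 0 | 20.0 points | 90.1% |
| 5% | 1.7% | 19.7 points | 89.3% |
| 10% | 3.3% | 19.3 points | 88.3% |
| 20% | 6.7% | 18.7 points | 86.3% |

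For g = 10%: (0.19333 − 1.96·0.06194)/0.06033 = 1.192, giving 88.3%.

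**4. The month 6 comparison alone.** Section 4.9.4 also reports by infusion time point. There f = g, so g = 10% gives 20.0 × 0.90 = 18.0 points. If the planning rates held at month 6, power would be (0.180 − 1.96·0.06134)/0.05993 = 0.997, or 84.1%. A 20-point gap at month 6 is itself an assumption. The Introduction reports 13.7% after Dose 2 of ocrelizumab in the earlier trials; against 14.3% the gap is 0.6 points, and 10% dilution would move it by 0.06 points.

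**5. The reverse route.** If 5% or 10% of comparator infusions were really ocrelizumab, the comparator rate would be 15.3% or 16.3%, the difference 19.0 or 18.0 points, and power 86.4% or 82.0%. These shares are also assumptions.

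Like the plan's own calculation, all power figures treat the records as independent with one per patient.

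**The case against.** The strongest reply is that this is a loose label and not a planned misattribution. The secondary reaction assessments in 3.3.1 and the infusion counts in 4.9.6 are worded by drug, Table 1 ties graded reactions to the ocrelizumab visits, and 4.7 keeps discontinuers under assessment for safety. The 95 v 95 calculation is tied in 4.9.6 to the first study infusion, where dilution is essentially nil. Section 4.1 also replaces switching-group dropouts before month 6. Much of this stands. It limits the size of the problem and shows that the intent was probably by drug. It does not settle the rule: the primary endpoint is by study group, intent to treat is stated twice, and the two sets of wording conflict.

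Three stronger inferences are tempting, and the documents do not support them:

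- **That the rituximab option at T3 dilutes the reaction endpoint.** No reaction is graded at T3, and the blood is drawn before any infusion.
- **That patients who react are the ones most likely to return to rituximab, so that an excess is hidden.** Nothing in the documents says who reverts.
- **That 10% to 15% of switching-group infusions could be rituximab, taking power to 84% or 80%.** With only T2 exposed, that requires 30% to 45% of patients to revert before month 6.

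The crossing in 4.1 is also not a case of rituximab counted as ocrelizumab. Under strict intent to treat it runs the other way. On a natural reading, with a new consent, each period's data follow the drug then given.

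A fair objection also applies to an over-simple remedy. Antibodies to ocrelizumab in a patient who has stopped it still result from ocrelizumab exposure, so moving those samples out of the main rate could understate immunogenicity.

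**Conclusion.** The concern holds as a conflict in the stated analysis rule. Intent to treat has no randomisation to protect here, is undefined, disagrees with the by-drug wording elsewhere and, taken literally, misplaces some infusions and samples. It does not hold as a claim that the plan sets out to count rituximab infusions as ocrelizumab results, or that a large excess would be hidden.

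The effect on the pooled primary comparison is probably small: about 0.7 points and 2 points of power if 10% of patients revert before month 6. The month 6 comparison takes the full 10% dilution, to 18.0 points, if the planning rates hold there. These sizes rest on an assumed reversion rate, on the plan's 34.3% and 14.3%, and on only T2 being exposed. The actual effect cannot be computed from the documents.

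**What to change.** Replace intent to treat in 4.1 and 4.9.4 with these rules:

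- **Reactions.** Every infusion started is analysed under the drug actually infused. A patient who contributes to both groups is counted, at each infusion, under the drug given at that infusion.
- **Disposition.** All enrolled patients stay in the disposition table, including those who stop ocrelizumab or are replaced.
- **B-cell depletion.** Each sample is attributed to the most recent anti-CD20 drug, and samples taken after a return to rituximab are listed separately.
- **Antibodies to ocrelizumab.** Every ocrelizumab-exposed patient stays in the main rate. Samples taken after a return to rituximab are flagged in a sensitivity listing.

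The cost is a few sentences in the plan and slightly fewer infusions labelled as switching-group. No new assessment is needed, since nurses already grade every infusion of either drug, and no treatment changes.
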